PBMC Peripheral Blood Mononuclear Cells
PFGE Pulsed Field Gel Electrophoresis
P1NP Procollagen-1 N-terminal propeptide
QPS Qualified Presumption of Safety
MIP-1 α Macrophage Inflammatory Protein-1 α

SPC Summary of Product Characteristics; in Dutch: officiële productinformatie IB1-tekst

Sponsor The sponsor is the party that commissions the organisation or performance of the

research, for example a pharmaceutical

company, academic hospital, scientific organisation or investigator. A party that provides funding for a study but does not commission it is not regarded as the

sponsor, but referred to as a subsidising party.

TLR Toll Like Receptor
TLR4 Toll like receptor 4

TNFα Tumour necrosis factor alpha

UAVG Dutch Act on Implementation of the General Data Protection Regulation; in Dutch:

Uitvoeringswet AVG

URTI Upper Respiratory Tract Infection

U.S. United States

V Visit wk Week

WMO Medical Research Involving Human Subjects Act; in Dutch: Wet Medisch-

wetenschappelijk Onderzoek met Mensen

NL81499.028.22 BOFEI

SUMMARY

Rationale:

Osteopontin (OPN) is a phosphorylated glycoprotein that is present in human milk and bovine milk. It has been shown to be involved in immune function. Arla Foods Ingredients has isolated a protein fraction from bovine milk which is rich in OPN, which is now commercially available as Lacprodan® OPN-10. In infants, supplementation with Lacprodan® OPN-10 is well tolerated, with clinically proven immunomodulatory outcomes such as downregulation of inflammatory cytokines and increases in T-cells and monocytes. Potential beneficial effects of Lacprodan® OPN-10 in adults and elderly have not yet been studied. During aging, the immune system undergoes profound decline, and specifically the responsiveness of the Th1-cell is attenuated. Given that OPN is a key factor in the Th1-response, this provides a potential for Lacprodan® OPN-10 to be a protein ingredient that is beneficial for immune health in both infants and the elderly. The current study design therefore aims to investigate the potential immune effects of Lacprodan® OPN-10 in elderly.

Objectives:

Primary objective:

Assess the percentage of responders to hepatitis B vaccination (i.e. attaining anti-hepatitis B antibody titres beyond 10 IU/L) in healthy elderly receiving a daily dose of Lacprodan® OPN-10, compared to a placebo product.

Secondary objectives:

- Compare the changes in serum anti-hepatitis B antibody titres between treatment groups
- Compare the change in circulating cytokines between treatment groups
- Quantify plasma levels of human and bovine OPN at baseline, and after intervention
- Determine whether intake of OPN-10 affects plasma levels of human OPN.
- Compare the change in serum LPS binding protein (LBP) between treatment groups
- Compare the incidence of infections during the trial, including specific upper and lower respiratory tract infections, between treatment groups
- Assess the safety of the selected intervention dose, including effects on markers of bone remodelling

Study design:

The study is designed as a double-blind, randomized, placebo-controlled trial, with two parallel treatment arms. After an 8-week intervention period, all subjects will receive a hepatitis B vaccination, at weeks 8, 10 and 12. Vaccination response will be measured at weeks 12 and 14. The intervention will be continued until the end of the study at week 14.

Study population:

Healthy, non-smoking men and women aged ≥60y and BMI 22-30, with anti-hepatitis B antibody titer ≤ 4 IU/L.

Intervention:

The active treatment consists of Lacprodan OPN-10, in the form of powder, that will be provided in 2 sachets in a dose of 2,5g/day for subjects weighing lower than 70 kg at screening, and a dose of 3,2g/day for subjects weighing 70 kg or more at screening. The sachets will be taken twice a day, with a meal.

The placebo treatment consist of powder in which Lacprodan® OPN-10 is replaced by maltodextrin, Total duration of the intervention is 14 weeks.

Main study parameters/endpoints:

- Anti-hepatitis B antibody titre
- Serum cytokines
- Plasma OPN (bOPN and hOPN)
- Serum LPS-binding protein (LBP)
- Infection incidence
- Clinical chemistry and hematology
- Serum P1NP and CTX1 (bone modelling markers)

Nature and extent of the burden and risks associated with participation, benefit and group relatedness:

The subjects will not benefit directly from participation in this study, apart from receiving a subject fee for their time investment plus reimbursement of traveling expenses.

Potential risks could be related to a) study product, b) study procedures or c) non-investigational product (hepatitis B vaccination).

Lacprodan® OPN-10 has a GRAS notification, based on the views of an independent Expert Panel and it is considered safe for the use by infants by the EFSA NDA Panel. Standard safety evaluations have shown no indications for potential risk involved with consumption. The dose administered in this study is 3.3% of the NOAEL calculated in safety studies.

The burden imposed by study procedures includes the daily intake of the study product, the (7) visits to the research location, the blood sampling (at 6 visits), faecal sample collection (3 times) and the vaccination injection (3 times). The collection of blood samples may produce discomfort or minor bleeding and the possibility of bruising at the site of the needle puncture. There is also a slight risk of infection at the site of the needle puncture. Side effects of hepatitis B vaccination that are reported to occur often or very often are: loss of appetite, irritability, headache, gastrointestinal symptoms (e.g., nausea, vomiting, diarrhea, abdominal pain), pain and redness at the injection site, fatigue, fever, malaise. Less common side effects include dizziness, myalgia, and influenza-like symptoms. Overall, the risks associated with participation in this study are considered small.

1 INTRODUCTION AND RATIONALE

1.1 Osteopontin in infant formula

Osteopontin (OPN) is a highly phosphorylated glycoprotein that is present in human milk and bovine milk. OPN is involved in many physiological processes, such as for instance, biomineralization, bone and tissue remodelling, wound healing and immune function. It is expressed in various tissues and cell types, including epithelial cells and immune cells.

Arla Foods Ingredients (AFI) has isolated a protein fraction from bovine milk which is rich in OPN. This product, Lacprodan® OPN-10, has a protein content ranging between 86-90% (based on nitrogen (N) factor of 7.17), of which 95% is OPN. Several pre-clinical and one clinical study have been performed with this ingredient. The clinical study was performed in infants (Lonnerdal et al. 2016; West et al. 2017; Jiang et al. 2019). Lacprodan® OPN-10 in dosages of 65 mg/L or 130 mg/L was shown to be well tolerated in infants (Lonnerdal et al. 2016). In the same study, it was shown that OPN downregulates TNF-α in infants which had received infant milk formula with Lacprodan® OPN-10 when compared to infants who had received regular infant milk formula without Lacprodan® OPN-10. Although antibody response to tetanus vaccination was not increased (Lonnerdal et al. 2016), it was shown that infants which had received the formula with 130 mg/L Lacprodan OPN-10 had increased T-cell proportions compared with infants which had received infant milk formula with a lower dosage (65 mg/L) or the control formula (West et al. 2017). Furthermore, monocyte proportions were higher in the infants receiving Lacprodan OPN-10, when compared to the breast-fed reference group. Higher plasma levels of human OPN were observed in infants receiving the infant milk formula with bovine Lacprodan OPN-10 when compared to infants receiving the control formula, suggesting that bovine Lacprodan OPN-10 promotes the synthesis or secretion of endogenous human OPN (Jiang et al. 2019).

Potential immunomodulatory or other potentially beneficial physiological effects of Lacprodan OPN-10 in adults have not yet been studied. During aging, the immune system undergoes profound decline (Simon et al. 2015), and specifically the responsiveness of the Th1 cells is attenuated. Given that OPN is a key factor in the Th1-response, this provides a potential for Lacprodan® OPN-10 to be a protein ingredient that is beneficial for immune health also in the elderly. The current study design therefore aims to investigate the potential immune effects of Lacprodan OPN-10 in elderly.

1.2 Proposed mechanism of bovine versus human OPN

Osteopontin (hOPN) is a multifunctional protein involved in a wide range of bioactivities, including cell proliferation and differentiation, immunomodulatory functions, biomineralization, as well as myelination (Jiang et al. 2020). OPN exerts its multiple functions by binding to its receptors on cell membranes, activating various cell signalling pathways. It can be produced by a variety of cell types including epithelial cells and immune cells.

Human OPN exists in two forms: secreted OPN present in body fluids and intracellular OPN found in immune cells. Secreted OPN appears in most body fluids, such as milk, urine, blood, saliva, and bile.

hOPN is present at a high concentration in human milk, \sim 178 mg/L in colostrum and \sim 134 mg/L in transitional milk.

Bovine OPN (bOPN) has been shown to stimulate immune development in a similar way as endogenous OPN in young animals (Jiang et al. 2020), and LPS-injected piglets tended to have a lower incidence of diarrhoea after bOPN intake (Ren et al. 2019). In a study in piglets, an increased response to influenza vaccination has been observed after bOPN administration (Donovan 2012) Concentrations of bOPN in bovine milk and infant formula are markedly lower than in human milk, around 18 and 9 mg/L, respectively (Schack et al. 2009; Jiang et al. 2020).

No studies have been reported on the effect of oral ingestion of bOPN in adult humans. In adult mice, OPN intake reduced DSS induced weight loss and neutrophil activity (Kanwar et al. 2016).

The safety of Lacprodan® OPN-10 has been extensively evaluated (Kvistgaard et al. 2014; Matulka 2017; EFSA NDA Panel 2022) and there are no indications that adverse effects could occur. However, higher plasma levels of human OPN were observed in infants receiving infant milk formula with bovine Lacprodan® OPN-10 when compared to infants receiving a control formula (Jiang et al. 2019). It was postulated that small amounts of undigested bOPN are absorbed and, by similarities in amino acid sequences, promoted the synthesis or secretion of endogenous hOPN. The presence of high levels of hOPN is associated with inflammatory conditions, and cellular senescence and other potentially adverse effects. It is unknown how the administration of bOPN will affect the circulating levels of hOPN in elderly. This is one of the secondary research questions to be answered in this study.

The beneficial effects observed for bOPN consumption in infants and piglets lead us to hypothesize that bOPN will strengthen the immune response in elderly, without increasing markers of inflammation. Given the results of the piglet study (Donovan 2012) in which an increased antibody response to influenza vaccination was observed, we have chosen a vaccination response model to evaluate the potential immune modulating characteristics of bOPN.

1.3 Vaccination response model

In their Guidance on the substantiation of health claims (EFSA NDA Panel (EFSA Panel on Dietetic Products 2016), EFSA states that an increase in the number of responders to vaccination (i.e. attaining antibody titres beyond a cut-off value which is considered to protect against the infection) is an appropriate outcome variable for the scientific substantiation of claims related to immune defence against pathogens.

When administering a vaccination challenge, it is preferable to use a vaccine with no previous exposure. If previous exposure has taken place, which may occur in the case of an influenza vaccination, there is a risk of boosting the previous vaccination with the challenge, which has a different mechanism and has different kinetics.

Hepatitis B vaccination has been used previously to study the immune modulatory effects of a dietary intervention (Albers et al. 2003). In that study, the hepatitis B vaccination was used to mimic a primary viral infection capable of inducing both humoral and the cellular responses. Standard vaccination schedules yield protection rates of 94 – 99% (Coates et al. 2001), with lower responses in older persons (> 40 y). Albers et al (Albers et al. 2003) used an accelerated vaccination schedule to provide a suboptimal trigger to the immune system, reasoning that this would be more reflective of natural infections and would leave room for improvement of the response due to the supplementation with the dietary ingredient. The response rates observed were indeed lower than with standard vaccination schedules. For hepatitis B antibodies, a cut-off value has been agreed (>10 IU/L) that is considered to protect against infection.

1.4 Hypothesis

Based on the results of this hepatitis B vaccination study (Albers et al. 2003), we have designed a randomized controlled intervention study, with a suboptimal vaccination challenge, in a population of healthy elderly men and women, with no prior hepatitis B vaccination or infection.

We hypothesize that, in a group of elderly subjects receiving Lacprodan® OPN-10 in a dose of 40 mg/kg body weight per day, the protective anti-HepB antibody titre is attained in a statistically significantly higher % of subjects compared to subjects receiving a placebo product.

1.5 Secondary research questions

As mentioned in section 1.1, OPN has been shown to downregulate inflammatory cytokines (TNF- α) in infants (Lonnerdal et al. 2016). In a healthy adult population, it is not expected that the level of circulating cytokines would be affected by a dietary intervention. However, an effect might be observed in elderly, as the immune system in elderly in general functions less well and markers of inflammation (low-grade) are on average increased in elderly. The effect of OPN-10 on inflammatory cytokines will therefore be addressed in this study.

In addition, a specific form of hOPN has shown the capability to bind LPS and hence may potentially lower low-grade inflammation (Ge et al. 2014). Serum LPS-binding protein (LBP), considered a more stable marker of microbial translocation as compared to LPS, will be analysed to investigate this potential effect of OPN-10 intervention. In healthy older individuals, higher levels of LBP were found to be associated with worse physical function and inflammation (Stehle et al. 2012).

Human OPN influences bone homeostasis by inhibiting mineral deposition and stimulating osteoclast activity (Standal et al. 2004; Nagao et al. 2011), which potentially might result in lower bone mass or bone density. Markers of bone formation (P1NP) and resorption (CTX-1) will be assessed to monitor Lacprodan® OPN-10's effects on bone homeostasis (Szulc et al. 2017).

2 OBJECTIVES

2.1 Primary Objective:

To assess the percentage of responders to hepatitis B vaccination (i.e. attaining anti-hepatitis B antibody titres beyond 10 IU/L) in healthy elderly receiving a daily dose of Lacprodan® OPN-10, compared to a placebo product.

2.2 Secondary Objectives:

- Compare the change in serum anti-hepatitis B antibody titres from baseline (V1) to 14 days after the second vaccination (V6) between treatment groups
- Compare the change in serum anti-hepatitis B antibody titres from baseline (V1) to 14 days after the third vaccination (V7) between treatment groups
- Compare the change in circulating cytokines from baseline to 8 weeks intervention (V4) and at the end of the study (V7) between treatment groups
- Quantify plasma levels of hOPN and bOPN at baseline, and at 4 weeks and 8 weeks intervention
- Determine whether intake of OPN-10 affects plasma levels of hOPN.
- Compare the change in serum LPS binding protein (LBP) from baseline to 8 weeks intervention between treatment groups
- Compare the incidence of self-reported URTI or LRTI during the trial, between treatment groups using weekly reports of symptoms related to upper and lower respiratory tract infections Assess the safety of the selected intervention dose, including effects on markers of bone remodelling

2.3 Exploratory Objectives:

[figure not shown]
- Compare the change from baseline in plasma brain-derived neurotrophic factor (BDNF) after 8 weeks intervention between treatment groups (optional)
- Compare the change in faecal microbiota composition after 8 and 14 weeks intervention between treatment groups (optional)

3 STUDY DESIGN

The study is designed as a double-blind, randomized, placebo-controlled trial, with two treatment arms.

After an 8-week intervention period, all subjects will receive a hepatitis B vaccination, administered by intramuscular injection, at weeks 8, 10 and 12. Vaccination response will be measured at weeks 12 and 14. The intervention will be continued until the end of the study at week 14.

NL81499.028.22 BOFEI

The study will be conducted at the clinical research facilities of NIZO in Ede and EBMR in Almere.. For the clinical conduct within these facilities, EB Medical Research (Almere) will be responsible. The responsibilities of EB Medical Research include the recruitment and screening of study subjects, conduct of the study visits and medical supervision.

The schedule of assessments at the different visits is as follows:

	V1	V2	V3	V4	V5	V6	V7
	Screening	Week 0	Week 4	Week 8	Week 10	Week 12	Week 14
		Day 0	Day 28	Day 56	Day 70	Day 84	Day 98
Screening	х						
Eligibility check	х						
Clinical conduct							
Randomization		Х					
Study product supply		Х		х	х	х	
HepB Vaccination				Х	Х	Х	
Blood sample collection		Х	X	X		X	Х
Serum anti HB titer	Х					X	X
Serum chemistry & hematology	Х	Х	X	X			
Plasma circulating cytokines		X		X			Х
Plasma/serum P1NP		Х		X			
Plasma/serum CTX-1		Х		X			
Plasma levels of OPN		X	X	X			
Serum LPS binding protein (LBP)		X		X			
Faecal sample collection		Х		Х			х
OPTIONAL BDNF		Х	-	Х		-	
AE registration		Х	Х	Х	х	Х	Х

4 STUDY POPULATION

4.1 Population (base)

The study population will consist of healthy, non-smoking men and women aged ≥60y and BMI 22-30, with anti-hepatitis B antibody titer ≤ 4 IU/L. Subjects will be recruited from the general healthy population in the Netherlands, primarily from the local region around the study location (Ede).

4.2 Inclusion criteria

In order to be eligible to participate in this study, a subject must meet all of the following criteria:

Substantial

- 1. Age ≥60 and healthy
- 2. Self-reported regular Dutch eating habits as assessed by questionnaire (3 main meals per day)
- 3. Anti hepatitis B antibody titer ≤ 4 IU/L
- 4. Non-smokers (ex-smokers can participate)
- 5. BMI ≥22 and ≤30
- 6. In good health as assessed during screening, and the medical investigator's professional judgment
- 7. Adherence to habitual diet, no changes during study period
- 8. Signed informed consent

Procedural:

- 9. Ability to follow Dutch verbal and written instructions
- 10. Willing to accept disclosure of the financial benefit of participation in the study to the authorities concerned
- 11. Willing to accept use of all encoded data, including publication, and the confidential use and storage of all data for at least 15 years
- 12. Willing to comply with study procedures, including intake of study products and collection of stool and blood samples
- 13. Willingness to give up blood donation starting at screening and during the entire study

4.3 Exclusion criteria

A potential subject who meets any of the following criteria will be excluded from participation in this study:

Substantial

- 1. Prior HB vaccination or infection
- 2. Any vaccination in the past month or any scheduled vaccination during the study period
- 3. Acute infection in the past month

NL81499.028.22 BOFEI

- 4. Treatment with oral antibiotics within 2 months of the start of the study,
- 5. Serious progressive disease or non-stabilized chronic illness (e.g., diabetes mellitus, cardiac insufficiency, respiratory insufficiency, cancer, chronic kidney or liver disease)
- 6. History of cancer
- 7. Gastrointestinal disorders (e.g., inflammatory bowel disease)
- 8. Immunodeficiency or autoimmune disorder
- 9. Use of immunosuppressive drugs (e.g. cyclosporine, azathioprine, systemic corticosteroids, antibodies)
- 10. Allergy or hypersensitivity to milk proteins, or lactose intolerance
- 11. Unexplained weight loss or weight gain of > 3 kg in the 3 months prior to pre-study screening
- 12. Evidence of current excessive alcohol consumption (>4 consumptions/day or >20 consumptions/week) or drug (ab)use
- 13. Mental status that is incompatible with the proper conduct of the study
- 14.

Procedural:

- 15. Not having a general practitioner, not allowing disclosure of participation to the general practitioner or not allow to inform the general practitioner about abnormal results.
- 16. Participation in any clinical trial including blood sampling and/or administration of substances starting 1 month prior to study start and during the entire study.
- 17. Personnel of NIZO, EBMR or AFI, their partner and their first- and second-degree relatives.

4.4 Sample size calculation

Sample size calculation was based on a publication by Albers et al. (Albers et al. 2003). In this study (with another nutritional intervention), seroconversion after hepatitis B vaccination in the placebo group was 33%, and it was 63% in the active group. For the present study, we assumed seroconversion of 25% in the placebo group. To be able to detect a doubling of seroconversion (to 50%) in the active group, a sample size of 58 subjects per group was calculated (Sample Size Calculator (clincalc.com)), with an alpha of 0.05 and a power of 0.8. Taking into account a drop-out rate of ~15%, we propose to include 70 subjects per group.

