7.4 Summary of known and potential risks and benefits

The safety profile for Engerix-B is described in the SPC. Side effects that are reported to occur often or very often are: loss of appetite, irritability, headache, gastrointestinal symptoms (e.g., nausea, vomiting, diarrhea, abdominal pain), pain and redness at the injection site, fatigue, fever, malaise. Less common side effects include dizziness, myalgia, and influenza-like symptoms.

The benefit of the vaccination is the protection against hepatitis B virus infection. However, due to the accelerated schedule, seroprotection will be achieved for about 75% of the participants (h17316 smpc.pdf (geneesmiddeleninformatiebank.nl).

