10 STATISTICAL ANALYSIS

A detailed Statistical Analysis Plan (SAP) will be prepared and signed-off by an independent statistician, ultimately before database lock.

Descriptive information: all parameters studied will be described as mean and standard deviation when normal distribution has been ascertained. When the data are not normally distributed, descriptive values will be represented by median and interquartile range. In all cases the number of observations per parameter will be provided.

Throughout the study a p-value of lower than 0.05 will be considered to detect a statistically relevant difference, applying two-sided testing.

In the SAP, the intention-to-treat (ITT) population and the per protocol (PP) population will be defined. In a blind data review meeting the criteria for excluding specific subjects from the PP population will be applied.

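### Sections 4.4 and 7.4 give incompatible response rates for the same accelerated vaccination: 25% on placebo and 50% on active for sizing, but about 75% of participants in the benefit statement

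*Protocol*

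**What the plan says.** Section 4.4 starts from an earlier nutritional study in which "seroconversion after hepatitis B vaccination in the placebo group was 33%, and it was 63% in the active group". It then sets its own inputs: "For the present study, we assumed seroconversion of 25% in the placebo group". The target and sample size follow: "To be able to detect a doubling of seroconversion (to 50%) in the active group, a sample size of 58 subjects per group was calculated", "with an alpha of 0.05 and a power of 0.8". Section 10 adds "applying two-sided testing", and section 10.1 names Fisher's exact test. For attrition, section 4.4 says: "Taking into account a drop-out rate of ~15%, we propose to include 70 subjects per group".

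Section 7.4, on the risks and benefits of the vaccine, says that "due to the accelerated schedule, seroprotection will be achieved for about 75% of the participants". It cites the product information and names no age group, dosing interval or time of reading.

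Section 7.3 places protection at 10 IU/L. The primary endpoint uses the same cut-off, read two weeks after the third dose (8.1.1 and 10.1). Section 7.6 describes a single accelerated schedule, on days 57, 71 and 85. It justifies that schedule as a deliberately weak stimulus, so that the supplement can still improve the response.

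**The concern.** Under section 4.4 neither arm is expected to exceed 50% responders, yet section 7.4 expects about three quarters of all participants to respond. Section 4.4 does not define seroconversion. Because it sizes the trial for the primary comparison, the word has to mean a responder at 10 IU/L, which is what section 7.3 calls protection.

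Two things depend on the answer. The placebo rate and the effect are the two clinical assumptions behind the 58 per group, and the reason for a suboptimal schedule presupposes a low rate. The 75% is the benefit described to the ethics committee, and it bears on how many subjects will be told at the end that their coverage is insufficient (7.6). Section 4.4 does not mention the 75%, and section 7.4 does not mention the 25%.

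**Working it through.** **Inputs.** From 4.4: 25% placebo, 50% active, alpha 0.05, power 0.80, 58 per group, about 15% drop-out, 70 enrolled per group. From section 10: two-sided testing. From 10.1: Fisher's exact test. From 7.4: about 75% of participants. Every rate paired with the 75% below is an assumption, because the protocol gives none.

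**The plan's own figure.** The usual formula with pooled variance under the null is

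n = [z₀.₉₇₅·√(2p̄(1−p̄)) + z₀.₈₀·√(p₁(1−p₁) + p₂(1−p₂))]² / (p₂−p₁)², with p̄ = 0.375.

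n = (1.960 × 0.6847 + 0.8416 × 0.6614)² / 0.25² = 1.8986² / 0.0625 = 57.7, so 58 per group. Then 58 / 0.85 = 68.2, so 69, and 70 enrolled is consistent. The arithmetic is right. The question is the input.

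**Overall rates.** Section 4.4 implies (25% + 50%) / 2 = 37.5% responders. Section 7.4 says 75%, a ratio of 2.0. Among 140 subjects the expected number unprotected is 140 × 0.625 = 87.5, about 88, under 4.4, and 140 × 0.25 = 35 under 7.4.

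**What the planned effect becomes near 75%.** The planned odds ratio is (0.50/0.50) / (0.25/0.75) = 3.

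- If 75% is the placebo rate, the odds are 3. An odds ratio of 3 gives odds of 9, which is 90%. A doubling is impossible.
- If 75% is the average of the two arms, a 25-point gap means 62.5% vs 87.5%. For an odds ratio of 3, with placebo x and active 1.5 − x, the condition is 2x² + x − 1.5 = 0. This gives x = (√13 − 1)/4 = 65.1%, against 84.9%. A doubling would need 50% vs 100%.

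**Power.** Two-sided Fisher's exact test at 0.05, by full enumeration of the two binomials, 58 per arm:

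| Reading | Placebo vs active | Power |
|---|---|---|
| Section 4.4 | 25 vs 50% | 74% |
| 75% is the placebo rate | 75 vs 80% | 7% |
| | 75 vs 85% | 20% |
| | 75 vs 90% (odds ratio 3) | 48% |
| | 75 vs 95% | 83% |
| 75% is the two-arm average | 65.1 vs 84.9% (odds ratio 3) | 64% |
| | 62.5 vs 87.5% (25 points) | 85% |

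The 64% is 63.5% at the rounded rates shown and 63.1% at the unrounded ones. The 74% in the first row is below 80% because the sample size formula uses a normal approximation while the planned test is exact. That is separate from the present point. If all 70 per arm completed, 75 vs 90% would have 58% power and 75 vs 85% would have 25%.

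**Detectable rate.** Solving the same enumeration for 80% power at 58 per arm gives active rates of about 52% from a placebo rate of 25%, 60% from 33%, 76% from 50%, and 94.5% from 75%.

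**The case against.** The 25% is not arbitrary. It starts from 33% in an earlier trial that, according to section 1.3, used an accelerated schedule and saw lower responses than standard schedules give. The same section notes weaker responses above age 40, and this trial enrols people aged 60 or over. A rate somewhat below 33% is defensible. The 75% comes from product information and may refer to other ages, intervals or reading times. The faulty passage may therefore be the one sentence in 7.4. This is a fair inference, but the protocol does not say so: 7.4 speaks of the participants without any limit.

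A reader might also infer that the placebo rate will be 75% and that the trial is badly underpowered. The text does not support this. Section 7.4 speaks of participants, which covers both arms, and a 25-point gap around a 75% average would have more power (85%) than the planned comparison (74%). Nor would a ceiling on the responder rate make a null result uninterpretable, since the change in titre at Visits 6 and 7 is a prespecified secondary outcome analysed with mixed models.

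What remains is the conflict itself. The two figures are both fixed in the protocol and nothing reconciles them.

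**Conclusion.** The contradiction stands: 37.5% overall, with neither arm above 50%, against about 75%, for one schedule and one cut-off. At least one figure is wrong or does not apply to this trial at Visit 7. The protocol does not settle which, so it would go too far to say that the stated power holds only if 7.4 is wrong. The 75% may be correct for another population or time point.

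The consequences are conditional. If 4.4 is right, the benefit statement overstates expected protection about twofold. If 7.4 is nearer the truth, a rise from 25% to 50% is not what the trial will face, and the argument that a weak stimulus leaves space for a gain loses force. Power at 58 per arm could then be well below or somewhat above the plan, depending on whether 75% is the placebo rate or the two-arm average and on the active rate assumed.

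**What to change.** - Reconcile 4.4 and 7.4. In 4.4, justify the placebo rate for people aged 60 or over, for this schedule, and for a reading two weeks after the third dose.
- In 7.4, correct the 75% or label it as applying to a different population or time point. Align the subject information if it repeats the figure.
- In 4.4, replace the single claim of detecting a doubling with a short table of the difference detectable with the planned completers (58 per arm; 70 × 0.85 = 59.5) at placebo rates from 25% to 75%, calculated for Fisher's exact test.

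This costs some wording and a small table. It needs no extra subjects and no change to the vaccination schedule. The downside is that the stated power may become less favourable.

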8.5 Replacement of individual subjects after withdrawal

If subjects withdraw before visit 2, subjects will be replaced. Subjects not completing the study for any reason will be considered as drop-outs. Drop-out rate should not exceed 25% of enrolled subjects, a minimum of 105 subjects should complete the trial. Only when the drop-out rate exceeds 25%, drop-outs will be replaced to achieve the minimum number of subjects to complete the trial.

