10.1 Primary study parameter(s)

Subjects will be classified as responders and non-responders for antibody production. Responders are subjects with an anti HB antibody titer of ≥10 IU/L, non-responders have a titer < 10 IU/L. The difference in number of responders for hepatitis B-specific antibody production will be analyzed by Fisher's exact test.

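### Section 4.4 states 80% power at 58 per group, but the Fisher's exact test fixed in 10.1 gives about 74–76% there, and the 8.5 floor of 105 completers lies below the 116 that 4.4 requires

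*Protocol*

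**What the plan says.** Protocol 4.4 (Sample size calculation): "we assumed seroconversion of 25% in the placebo group". "To be able to detect a doubling of seroconversion (to 50%) in the active group", it continues, "a sample size of 58 subjects per group was calculated", "with an alpha of 0.05 and a power of 0.8". It cites a web calculator without naming the formula, allows for about 15% drop-out and enrols 70 per group. Section 10 makes all tests two-sided ("applying two-sided testing").

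Protocol 10.1 (Primary study parameter(s)): "The difference in number of responders for hepatitis B-specific antibody production will be analyzed by" Fisher's exact test. The choice of test is thus made in the protocol itself and is not deferred to the SAP.

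Protocol 8.5 (Replacement of individual subjects after withdrawal) caps drop-out at 25% of those enrolled, says that "a minimum of 105 subjects should complete the trial", and adds: "Only when the drop-out rate exceeds 25%, drop-outs will be replaced".

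**The concern.** Two things do not fit together. First, the sample size appears to have been calculated for one test and the analysis specified with another. Fisher's exact test is conservative at these sizes, so a size that gives 80% under an uncorrected approximation gives less under Fisher. Second, 4.4 needs 2 × 58 = 116 evaluable subjects, while 8.5 triggers no replacement until fewer than 105 would complete.

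This is the protocol's only power statement, and it concerns the single primary hypothesis. If it is too high, a non-significant result will be read as stronger evidence against an effect than it is. Readers of 8.5 may also take 105 completers to be adequate by the trial's own standard.

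**Working it through.** **Inputs.** Placebo 25%, active 50%, alpha 0.05, power 0.80, 58 per group, 70 per group enrolled, about 15% loss (4.4); two-sided testing (10); Fisher's exact test (10.1); 25% loss ceiling and 105 completers (8.5).

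**1. Reproducing 58.** The pooled formula without continuity correction is

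n = [1.96·√(2·p̄·(1−p̄)) + 0.8416·√(p1(1−p1) + p2(1−p2))]² / (p2−p1)², with p̄ = 0.375.

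n = [1.96·√0.46875 + 0.8416·√(0.1875 + 0.25)]² / 0.0625 = (1.3419 + 0.5567)² / 0.0625 = 57.7, so 58.

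The other common variants do not give 58: continuity-corrected 66 (65.4 rounded up), unpooled 55, one-sided 46. With 15% loss, 58 / 0.85 = 68.2, so 69; the planned 70 is consistent with that.

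**2. Power of the planned test.** For each pair of arm sizes, all outcomes of the two binomials (25% and 50%) were enumerated. The two-sided Fisher p-value was the sum of table probabilities no larger than the observed one, and the test rejects if p < 0.05. The uncorrected chi-square test was enumerated in the same way.

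| Placebo/active | Fisher | Uncorrected chi-square |
|---|---|---|
| 52/53 | 73.1% | 75.8% |
| 53/52 | 74.6% | 75.8% |
| 58/58 | 74.3% | 79.9% |
| 57/59 | 78.1% | 80.5% |
| 59/57 | 75.6% | 80.4% |
| 59/60 | 77.6% | 81.9% |
| 63/63 | 79.4% | 84.3% |
| 64/64 | 80.2% | 84.9% |
| 70/70 | 83.1% | 87.0% |

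At 58/58 and a common rate of 25%, the exact type I error is about 3.2% for Fisher and about 5.15% for the uncorrected chi-square test.

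**3. Averaging over arm splits.** Fisher power is jagged, and exactly equal arms tend to be low points. Completers were therefore also treated as a random subset of 70 + 70, and power was averaged over the resulting splits.

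| Completers | Loss from 140 | Fisher | Chance of missing the effect | Uncorrected chi-square |
|---|---|---|---|---|
| 105 | 25% | 73.7% | 26.3% | 76.5% |
| 116 | 17.1% | 76.4% | 23.6% | 80.6% |
| 119 | 15% | 78.2% | 21.8% | 81.5% |
| 128 | 8.6% | 81.9% | 18.2% | 84.4% |

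With equal arms, 80% is first reached at 64 per group: 128 completers, a loss of 12/140 = 8.6%. On the averaged basis it is first reached at 123 completers (80.3%), a loss of 17/140 = 12%. Both losses are smaller than the 15% planned.

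**4. The completer floor.** 140 × 0.75 = 105, against 2 × 58 = 116, a gap of 11. The 116 is lost once drop-out exceeds 24/140 = 17.1%. Between there and 25%, 8.5 provides for no replacement although the trial is below the size calculated in 4.4. This part does not depend on the choice of test.

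**The case against.** Several points on the other side are sound.

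- The 74.3% at 58/58 is a low point caused by discreteness. Averaged over splits of 116 completers, Fisher power is 76.4%. This stands, and both figures are given.
- The trial enrols 70 per group, not 58. At the planned 15% loss the shortfall is about 2 points, and with full follow-up Fisher power is 83.1%. A reader might infer that the trial cannot reach 80% power. The protocol does not support that: with small enough loss it can.
- A reader might put the chance of missing the effect at 30%. That needs 52/52 (70.3% power), which is 104 completers and below the protocol's own minimum.
- The 15% in 4.4 is a planning assumption and the 25% in 8.5 is a worst-case trigger. The protocol never says that 105 completers preserve 80% power, nor that 105 is the expected number. So 8.5 makes no false power claim. What remains is that it sets an acceptable minimum below the size 4.4 calculated, without stating the consequence.
- Fisher's test is a legitimate choice because it holds the 5% level, whereas the uncorrected chi-square test slightly exceeds it here. The criticism is of the stated power, not of the test.
- The origin of 58 is inferred. The match is exact, but the power of Fisher's test at 58 per group is the same whatever formula the calculator used.

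**Conclusion.** The 80% stated in 4.4 is wrong for the test that 10.1 fixes. At the calculated size the power is 74.3% with equal arms and about 76% averaged over splits. It is about 78% at the planned loss and about 74% at the accepted floor. The chance of missing the planned effect is therefore about 22–26% rather than 20%. Independently, the floor of 105 in 8.5 is 11 short of the 116 that 4.4 requires, and even the test that matches the calculation has only about 76% power there. The shortfall is modest and mostly correctable by wording.

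The figures take 25% versus 50% as true, use an unstratified comparison and analyse completers only. How drop-outs enter the intention-to-treat analysis may be defined in the SAP, which was not available. As an illustration only: if all 140 were analysed and a 15% loss were counted as non-response (0.85 × 25% = 21.25% versus 0.85 × 50% = 42.5%), Fisher power at 70/70 would be 72.7%.

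**What to change.** **Needed.** In 4.4, state the power for Fisher's exact test: 74.3% at 58 per group (about 76% averaged over splits of 116), about 78% at 119 completers and about 74% at 105. Name the formula behind the 58. In 8.5, put the power at 105 next to the floor. This costs wording and a less favourable stated power, and no extra subjects.

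**Optional.** Before unblinding, pre-specify a primary test that matches the calculation, with Fisher as a sensitivity analysis. The uncorrected chi-square test has 79.9% power at 58/58, at the price of an exact type I error of about 5.15% at a 25% rate. A stratified test was not evaluated, so these figures should not be carried over to one.

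**If the floor is revised,** it must fit the test that is kept: 116 for the uncorrected chi-square test, about 128 for Fisher with equal arms. Setting it at 116 while keeping Fisher would leave the shortfall in place. A higher floor has a recruitment cost, because drop-outs would have to be replaced once loss exceeds about 17% (116) or about 9% (128).
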